7.6.2 Concomitant Medications

Concomitant medications will be summarized by the WHO Drug substance name and listed by patient. Transfusions, colony-stimulating factors, corticosteroids, and erythropoietin stimulating agents will also be summarized by the WHO Drug substance name. Summaries will also be presented for the subset of patients who had any IRR reported, as well as for the subset of patients who had any immune-related AE reported.

7.6.3 Deaths

Summaries of deaths will be presented by dose regimen and overall. Deaths that occur within the safety reporting period (i.e., within 30 days of last study treatment with brentuximab vedotin or 100 days of nivolumab, whichever is later) will be presented, as well as deaths that occur beyond this time point. In addition, primary cause of death will be summarized by descending MedDRA preferred term (unless otherwise specified) and summarized by dose regimen and overall. Death information will be listed by patient.

8 INTERIM ANALYSIS

An SMC consisting of all Principal Investigators and the sponsor's Medical Monitor will monitor the trial for safety and efficacy and will convene periodically during the study.

In Part 1 of the study, an SMC will monitor the trial for safety and provide guidance regarding possible enrollment of additional patients in Part 1 and possible expansion of enrollment in Part 2. Initially 6 patients will be enrolled in Part 1. If a patient discontinues treatment for reasons other than a DLT prior to 6 patients completing the DLT evaluation period then they will be replaced (as long as the arm remains open). These patients will be monitored for DLT throughout the DLT evaluation period. The SMC will review safety data and provide recommendations when either of the following occurs:

- 1. 2 or more of the patients in the current arm are determined to have had a DLT based on the protocol definition.
- 2. 6 patients complete the DLT evaluation period (by either remaining on treatment or having a DLT).

On review of all available data, the SMC may determine that the classification of DLT was not appropriate for one or more of the patients, in which case enrollment may resume if the target of 6 patients has not yet been reached. However, if 2 or more patients were determined to have experienced DLT, then expansion will not occur as the next step. Based on SMC recommendations, additional patients may be enrolled at modified treatment and/or dosing levels. These additional patients will then be assessed for DLT in the same manner described above to determine if it is appropriate to expand enrollment. If it is determined by the SMC that due to safety concerns no additional dose levels or schedules should be enrolled, then the study will be closed to enrollment.

An ongoing real-time review of serious AEs (SAEs) in all parts of this study will be conducted by the Seattle Genetics Program Safety Monitoring Team.

Additionally, interim data from the study may be presented at scientific meetings such as the annual meetings of the American Society of Clinical Oncology and the American Society of Hematology.

9 CHANGES FROM PLANNED ANALYSES

9.1 Changes from the Original Protocol

There are no changes from the original protocol.

APPENDIX A: IMPUTATION OF PARTIALLY UNKNOWN ADVERSE EVENT DATES

The algorithm below should be used to impute pre-existing condition and adverse event (AE) start dates for which only partial information is known. For ease of reading, both pre-existing conditions and AEs will be referred to as AE for the remainder of this document. The algorithm should be applied to every AE record on a record by record basis. AE start dates should be imputed before imputation of AE condition end date in all cases. The AE condition end date should only be used in the imputation of the AE start date if it is a complete, known date.

AE day and month are missing

- If the year is the same as the year of first dose of investigational agent and the onset period and/or onset time indicate that the start of the AE was pre-dose:
 - AE start date will be imputed as the minimum of (AE condition end date*, day prior to first dose of investigational agent)
- If the year is the same as the year of first dose of investigational agent and the onset period and/or onset time indicate that the start of the AE was post-dose:
 - AE start date will be imputed as the minimum of (AE condition end date*, first dose date of investigational agent)
- If the year is before the year of first dose of investigational agent:
 - AE start date will be imputed as the minimum of (AE condition end date*,
 December 31st see example 2 below)
- If the year is after the year of first dose of investigational agent:
 - AE start date will be imputed as the minimum of (AE condition end date*,
 January 31st see example 2 below)

AE month only is missing

 Treat day as missing and replace both month and day according to the above procedure

AE day only is missing

- If the month/year is the same as the month/year of first dose of investigational agent and the onset period and/or onset time indicate that the start of the AE was pre-dose:
 - AE start date will be imputed as the minimum of (AE condition end date*, day prior to first dose of investigational agent)
- If the month/year is the same as the month/year of first dose of investigational agent and the onset period and/or onset time indicate that the start of the AE was post-dose:
 - AE start date will be imputed as the minimum of (AE condition end date*, first dose date of investigational agent)

- If the month/year is before the month/year of first dose of investigational agent:
 - AE start date will be imputed as the minimum of (AE condition end date*, last day of the month)
- If the month/year is after the month/year of first dose of investigational agent:
 - AE start date will be imputed as the minimum of (AE condition end date*, last day of the month)

The following algorithm should be used to impute AE condition end dates. The AE records for a condition/event should be sorted by the imputed start dates then record position (order of entry into the eCRF). After sorting, if any condition end date month/year is greater than any subsequent record end date month/year, then change the imputed start day only to end of month. Repeat as necessary.

After sorting the AE records, apply the following rules to partial or missing AE condition end dates:

For all records excluding the last chronological record for a condition/event

• AE condition end date will be imputed as the start date of the subsequent record

For the last chronological record for a condition/event

- If outcome is "recovered/resolved", "recovered/resolved with sequelae", or "fatal" apply the following:
 - o If only year is provided for the end date and year is equal to the year of the last dose date:
 - AE condition end date will be imputed as the minimum of (last dose date+30, death date, data extraction date, December 31st of the end date year)
 - o If only year is provided for the end date and year is not equal to the year of the last dose date:
 - AE condition end date will be imputed as the minimum of (death date, data extraction date, December 31st of the end date year)
 - o If month and year are provided for the end date:
 - AE condition end date will be imputed as the minimum of (death date, data extraction date, last day of the end date month/year)
- If outcome is "recovering/resolving", "not recovered/resolved", "unknown", or blank:
 - AE condition end date will not be imputed.

^{*} Only use condition end date if known and complete end date is available.

Example 1

AESPID 1: Condition/Event HEADACHE First dose date 01JAN2012

Prior to imputation

Start date	Condition end date	Severity	Outcome	Onset
UNUNK2011	15APR2012	1	not recovered/resolved	pre-ICF
15APR2012	UNMAY2012	2	recovering/resolving	post 1st dose
UNMAY2012	UNJUN2012	1	not recovered/resolved	post 1st dose
UNJUN2012	UNJUN2012	3	recovering/resolving	post 1st dose
UNJUN2012	10JUL2012	2	recovering/resolving	post 1st dose
10JUL2012		1	not recovered/resolved	post 1st dose

Post imputation

Start date	Condition end date	Severity	Outcome
31DEC2011	15APR2012	1	not recovered/resolved
15APR2012	31MAY2012	2	recovering/resolving
31MAY2012	30JUN2012	1	not recovered/resolved
30JUN2012	30JUN2012	3	recovering/resolving
30JUN2012	10JUL2012	2	recovering/resolving
10JUL2012		1	not recovered/resolved

Example 2 (highlights choice of last day of the month as opposed to the 1st or the 15th)

AESPID 4: Condition/Event NAUSEA First dose date 01APR2012

Prior to imputation

Start date	Condition end date	Severity	Outcome	Onset
UNUNK2011	25APR2012	1	not recovered/resolved	pre-ICF
25APR2012	UNAPR2012	2	recovering/resolving	post 1st dose
UNAPR2012	04MAY2012	1	recovered/resolved	post 1st dose

Post imputation

Start date	Condition end date	Severity	Outcome
31DEC2011	25APR2012	1	not recovered/resolved
25APR2012	31APR2012	2	recovering/resolving
31APR2012	04MAY2012	1	recovered/resolved

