7.6.1.1 Adverse Events of Special Importance

Adverse events of peripheral neuropathy, infusion related reactions, immune-related AEs, and other rare serious AEs may be considered AEs of special importance.

Resolution of selected adverse events will be defined as event status of recovered/resolved or recovered/resolved with sequelae; or return to baseline or lower severity as of the latest assessment for pre-existing events. The date of resolution is defined as follows: for events with an onset after the first dose date, if event outcome is "recovered/resolved" or "recovered/resolved with sequelae", then the date of resolution is the event end date; for events ongoing at baseline, if event severity returns to baseline severity or lower as of the last recorded severity, then the date of resolution is the date of severity change to baseline or lower severity.

For events that are not resolved, improvement is defined as decrease by at least one grade from worst grade as of the latest assessment. The date of improvement is defined as follows: for events that did not resolve and decrease by one grade or more from the worst post-baseline severity as of the last recorded severity (i.e., severity did not subsequently worsen), then the date of improvement is the start date when the post-baseline grade becomes lower than the worst grade for the first time without any subsequent grade(s) equal to the worst grade.

Time to resolution is computed from start date of first treatment emergent episode of the event or start date of newly onset event after first dose of treatment drug to date of resolution.

Time to improvement is computed from start date of the worst grade of the event. Time to resolution /improvement will be summarized at the event level.

For summaries of events or summaries of patients with events ongoing at EOT, EOT is defined as the EOT visit or 30 days after the last dose of either study drug.

Time to onset of treatment-emergent adverse events is defined as time from the date of first dose to start date of first treatment emergent episode of the event or start date of newly onset event after first dose of treatment drug. In the analyses of time to onset by grade, the events should be excluded where the specified grade only occurs after a higher grade.

Peripheral Neuropathy

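### SAP Appendix A can date a later, partly dated record of an adverse event to the first dose, so that it sorts ahead of the event's earlier record and distorts onset, duration and resolution dates

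*SAP*

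**What the plan says.** SAP 6.5 imputes AE dates to calculate event duration and treatment-emergent status; Appendix A gives the algorithm. Its worked examples show that one event may be stored as several severity records.

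- **Unit.** "The algorithm should be applied to every AE record on a record by record basis".
- **Triggers.** With the day missing: "If the month/year is the same as the month/year of first dose of investigational agent". With day and month missing: "If the year is the same as the year of first dose of investigational agent". Both branches need the onset to be flagged as post-dose.
- **Result of either trigger.** "AE start date will be imputed as the minimum of (AE condition end date*, first dose date of investigational agent". The end date counts only if it is complete.
- **Sort.** Records of an event are "sorted by the imputed start dates then record position (order of entry into the eCRF", so entry order only breaks ties.
- **Repair step.** "if any condition end date month/year is greater than any subsequent record end date month/year, then change the imputed start day only", to the end of the month.
- **End dates.** A partial or missing end on any record but the last becomes the start of the next sorted record. If the last record's outcome is recovering, not recovered, unknown or blank: "AE condition end date will not be imputed".

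These dates are used in SAP 7.6.1.1: "Resolution of selected adverse events will be defined as event status of recovered/resolved or recovered/resolved with sequelae". For events that begin after the first dose, a resolved outcome takes the event end date as its resolution date. Improvement compares the last recorded severity with the worst one. Time to onset by grade leaves out events in which that grade appears only after a higher grade.

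**The concern.** The first-dose rule suits the first record of an event. Applied to a later severity record, it ignores something already known: the record cannot start before the one it follows. If the preceding record has a complete start date after the first dose, the later record is moved ahead of it. The repair step shows that the authors foresaw ordering trouble, but its trigger is a strictly later end month and its action is limited to the day.

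At stake are the descriptive time courses of peripheral neuropathy and the other AEs of special importance: onset by grade, duration, and time to resolution or improvement. The error can go either way. A resolved event can lose its closing date, and an ongoing worsening can read as an improvement.

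**Working it through.** **Inputs.** All rules come from SAP Appendix A. Duration is end − start + 1 (SAP 6.4). The rules were coded in order: start date, sort, repair step repeated until stable, end date.

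**1. The SAP's own examples.** Example 1 reproduces exactly. In Example 2 (first dose 01APR2012), record 2 runs 25APR to UNAPR, recovering, and record 3 runs UNAPR to 04MAY, recovered.

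- Start of record 3 = min(04MAY, 01APR) = 01APR, which is before 25APR, so it sorts ahead of record 2.
- Its end month, May, is later than April, so the repair step moves its start to the end of April.
- The order is then 1-2-3 and the event resolves on 04MAY. This matches the SAP, except that it prints 31APR2012, a date that does not exist; the rule gives 30APR2012.

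**2. One change: record 3 ends 29APR2012.**

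- Start of record 3 = min(29APR, 01APR) = 01APR.
- April is not later than April, so the repair step does not act.
- The order is 1-3-2. Record 3 (Grade 1, recovered) runs 01APR to 29APR. Record 2 (Grade 2, recovering) is last, from 25APR, with no end date.

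**3. Other constructed cases, first dose 01APR2012.**

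| Case | Records as entered | Repair step | Derived result |
|---|---|---|---|
| A | Grade 1, 10APR to UNAPR, not recovered; Grade 3, UNAPR to 28APR, recovered | does not act | Grade 3 01APR to 28APR; then Grade 1 from 10APR, no end |
| B | Grade 2, 10APR to UNAPR, recovering; Grade 1, UNAPR to UNAPR, recovered | does not act | Grade 1 01APR to 10APR; then Grade 2 from 10APR, no end |
| C | Grade 2, 10MAY to UNJUN, recovering; Grade 1, UNUNK2012 to 20JUL, recovered | acts, but reaches only 30APR | Grade 1 30APR to 20JUL; then Grade 2 from 10MAY, no end |
| D | Grade 2, 10MAY to UNUNK2012, recovering; Grade 1, UNUNK2012 to 20JUL, recovered | does not act | Grade 1 01APR to 20JUL; then Grade 2 from 10MAY, no end |
| E | Grade 1, 10APR to UNAPR, not recovered; Grade 3, UNAPR to blank, not recovered | does not act | Grade 3 01APR to 10APR; then Grade 1 from 10APR |

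Case A moved one month later is ordered correctly, so the fault lies in the first-dose branch. If the earlier record starts on the first-dose date itself, the tie is broken correctly by entry order.

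**4. What this does to the summaries.**

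- Case A: the event began on 10APR but is dated 01APR, 9 days early. If the recovered record still closes the event, time to resolution is 28 − 1 + 1 = 28 days instead of 28 − 10 + 1 = 19. Grade 3 onset moves to Day 1, and Grade 1 leaves the Grade 1 onset analysis because it now follows Grade 3.
- Case E: an ongoing Grade 3 worsening is closed on 10APR, and the last severity is Grade 1. Under 7.6.1.1 that reads as improved.

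**5. How often.** The documents do not say how many records have partial dates, so every rate here is conditional on assumptions.

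- Resolved two-record events whose second record starts in the first-dose month with the day unknown, with exponential record lengths of mean 3/5, 5/7, 7/14 and 14/28 days: 67%, 57%, 38% and 22% end with an unresolved record last.
- Same lengths, every second record still lacking its day, but onset spread evenly over 163 days (63 days from first to fourth dose plus 100): 4.9%, 3.6%, 2.3% and 0.8%. These must then be multiplied by the unknown share of partial dates.
- A separate grid of assumed dates, second record lasting 3 to 30 days: 10% to 33% for day-missing starts and 72% for year-only starts.

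**The case against.** The strongest reply is that Appendix A changes dates, not outcomes. In cases A, C and D the recovered record keeps its complete end date; only the earlier record stays open. SAP 7.6.1.1 does not say which record supplies the event outcome. A reader might infer that the plan turns resolved AEs into ongoing ones outright, but the documents do not support that as a general statement. It follows only if the last sorted record is decisive. This part of the reply stands. It does not rescue the reversed order, the wrong onset and durations, or case E, because improvement does depend on the last recorded severity.

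A reader might also infer that the primary safety endpoint is compromised. It is not. Re-ordering severity records alters no AE's type, incidence, maximum grade, seriousness or relatedness. Treatment-emergent status rests first on the onset-period field, then on term and grade (Appendix B).

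The year-only case C is fair to question: in both worked examples each record starts where the previous one ends, at the same precision, so UNJUN followed by UNUNK2012 would be unusual. Case D and the day-missing cases keep that pattern and still fail.

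Finally, 22% to 67% might be read as a share of all AEs. It describes only an assumed vulnerable subset.

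**Conclusion.** The fault is real and follows from the SAP's own text: a one-date change to Example 2 produces a wrong order. It needs a later post-dose record of the same event, partly dated in the first-dose month (or by year only in the first-dose year), following a record that starts after the first dose. The repair step must also miss it, through equal end months, an end without a month, or a wrongly imputed month.

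In those cases the severity course, onset by grade, duration and time to resolution or improvement are wrong, and the earlier record can be left last with no end date. Whether a resolved AE also reads as unresolved depends on a choice that the SAP leaves open. Incidence, maximum grade, treatment-emergent status and the CR test are unaffected. The number of affected records is unknown and probably small, so this is a worthwhile correction of minor weight.

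**What to change.** In SAP Appendix A, process the records of an event in eCRF order and keep the current start rule, with one added condition. If a partly dated record's imputed start would precede the start of the preceding record of the same event, reset it:

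- to the last day of its known month, or to the preceding record's start date if the month is unknown;
- capped at its own complete end date;
- never outside its known year;
- never before the first dose for a post-dose record.

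Keep the sort by start date with eCRF order as tie-breaker. Sorting purely by entry order would override complete dates, and using the preceding start without these limits could ignore a known year or place a post-dose record before the first dose. Correct 31APR2012 to 30APR2012 in Example 2.

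Coded this way, both worked examples are unchanged apart from 30APR. Example 2 ending 29APR resolves on 29APR; A resolves on 28APR, B on 30APR, C and D on 20JUL; E stays an ongoing Grade 3 event. The existing repair step had nothing left to do in any of these cases.

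The cost is a few lines of SAP text and program, with no new data and no protocol amendment. The date of the severity change stays approximate: in case A, Grade 3 is placed on 28APR, its own end date.

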### **7.6.1.3 Reporting Periods for Adverse Events and Serious Adverse Events**

The safety reporting period for all AEs and SAEs is from study Day 1 (predose) through the EOT visit or 30 days after the last brentuximab vedotin dose or 100 days after the last nivolumab dose, whichever is later. However, all study protocol-related AEs are to be recorded from the time of informed consent. All SAEs that occur after the safety reporting period and are considered study treatment-related in the opinion of the investigator should also be reported to the sponsor.

SAEs will be followed until significant changes return to baseline, the event stabilizes (recovering/resolving) or is no longer considered clinically significant by the investigator, or the patient dies or withdraws consent. All non-serious AEs will be followed through the safety reporting period. Certain non-serious AEs of interest may be followed until resolution, return to baseline, or study closure.

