6.4 Data Transformations and Derivations

No data transformations are planned for the primary endpoints.

Reported age in years will be used; if not available, age in years will be calculated with the SAS INTCK function (with method specified as "continuous") using informed consent date and birth date.

Study Day will be calculated as (Date - First Dose Date + 1) for dates on or after the first dose date. For dates prior to the first dose date, Study Day will be calculated as (Date - First Dose Date). For all calculations of Study Day, the First Dose Date will be the earliest date of treatment administration for any study drug.

Other time variables based on two dates, e.g., Start Date and End Date, will be calculated as (End Date - Start Date + 1) (in days) unless otherwise specified in the planned analysis section.

The following unit conversion will be implemented unless otherwise specified:

Months = Days / 30.4375

Years = Days / 365.25

Baseline values used in all analyses will be the most recent non-missing measurement prior to the first dose of study drug.

The end-of-treatment (EOT) date will be the date the EOT visit is performed; if an EOT visit is not performed then the EOT date will be either the EOS date or 30 days after the last dose of any study drug, whichever is earlier.

For efficacy assessments, the date of response will be the latest of all radiologic scan dates for the given restage assessment. The date of progression will be the earliest of all radiologic scan dates for the given restage assessment, or the date of investigator claim of clinical progression. An adequate tumor assessment to determine response must include a radiologic(CT) scan and a PET scan. Determination of progression by radiologic assessment may be based on CT or PET alone if there is clear evidence of PD by one of these modalities. While a radiologic assessment to confirm progression is strongly preferred, an investigator claim of clinical progression is adequate for an assessment of PD.

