6.5 Handling of Dropouts and Missing Data

With the exception of AE dates, missing data will not be imputed.

AE dates will be imputed for the purpose of calculating duration of events and treatmentemergent status (see Appendix A for imputation details and Appendix B for treatmentemergent definition). Censoring for time-to-event endpoints will be described in Section 7.5. with each planned analysis, as applicable.

Patients whose disease response cannot be assessed will be scored as non-responders for calculating the CR rate and ORR. Patients with missing values of a variable other than response endpoints (CR and ORR) and time-to-event endpoints (PFS and OS) will be excluded from the analysis of that endpoint unless otherwise specified.

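### SAP Appendix A can impute an AE end date that falls before the AE's start date, giving zero or negative durations in a small number of records

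*SAP*

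**What the plan says.** SAP 6.5 gives the purpose of the algorithm: "AE dates will be imputed for the purpose of calculating duration of events", and also for treatment-emergent status. SAP 6.4 sets the default for an interval between two dates: it "will be calculated as (End Date - Start Date + 1) (in days".

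Appendix A imputes start dates first. If only the day is missing and the month is after the first-dose month, "AE start date will be imputed as the minimum of (AE condition end date*, last day of the month". The end date in that minimum "should only be used in the imputation of the AE start date if it is a complete, known date", so a partial end date cannot pull the start back.

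End dates follow. For the last chronological record of an AE that resolved, resolved with sequelae or was fatal, two branches matter here:

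- Only the year is known, and it is the year of last dose: "AE condition end date will be imputed as the minimum of (last dose date+30, death date, data extraction date", with 31 December of that year as the remaining term.
- Month and year are known: "AE condition end date will be imputed as the minimum of (death date, data extraction date, last day of the end date month/year".

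Protocol 7.6.1.3 runs AE collection to the EOT visit, 30 days after brentuximab vedotin, "or 100 days after the last nivolumab dose, whichever is later". SAP 7.6.3 applies the same 30/100-day period to deaths. Under SAP 7.6.1.1, for an event that began after first dose and resolved, "then the date of resolution is the event end date". The same section commits to summarising time to resolution of peripheral neuropathy.

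**The concern.** A minimum has no lower bound. The year-only branch caps the end at 30 days after last dose, but events are collected well beyond that, and no step compares the imputed end with the start. The month-and-year branch has a related weakness: the start is pushed to the month end while the end is pulled back to death or data extraction.

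In both cases the algorithm, followed exactly, returns an end before the start. The output at stake is AE duration and, in a narrow set of cases, time to resolution of neuropathy. Without a written rule, the programmer has to choose a repair after seeing the data.

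**Working it through.** The documents give no figure for this rule, so the appendix's own examples are the first check. Example 1 reproduces. Example 2 reproduces once 31APR2012, which is not a calendar date, is read as 30APR2012. Neither example covers the two branches below.

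**Inputs.** L = last dose date, taken as the last dose of any study drug (Appendix A does not define it). End = min(L + 30, death, data extraction, 31 December), from Appendix A. AE collection runs to L + 100 if nivolumab was given on L, from Protocol 7.6.1.3. Duration = End − Start + 1, from SAP 6.4.

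**Route 1: year-only end date in the last-dose year.** With a complete start at L + k:

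duration ≤ (L + 30) − (L + k) + 1 = 31 − k

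| Onset day k | Duration at most |
|---|---|
| 30 | 1 |
| 31 | 0 |
| 70 | −39 |
| 100 | −69 |

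If both drugs stop together, 70 of the 100 post-dose onset days (31 to 100) are exposed. Two things narrow this:

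- *Calendar.* Onset must fall in the last-dose year. Day 31 needs a last dose by 30 November, and day 100 needs one by 22 September. A last dose on 15 October leaves a range of 0 to −46, one on 20 November leaves 0 to −10, and one after 30 November leaves nothing.
- *Nivolumab stopped early.* Assume on-schedule dosing, with brentuximab vedotin last given on Cycle 4 Day 1 (study day 64). If nivolumab was given only on Cycle 1 Day 8, collection ends at 8 + 100 − 64 = L + 44, so 14 days are exposed (31 to 44). If it was given only on Cycle 1 Day 1 in Part 3, collection ends at 1 + 100 − 64 = L + 37, so 7 days are exposed (31 to 37).

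The figure −69 is not a limit. With last dose on 1 June and a start known only as September, the start becomes 30 September and the end 1 July. The duration is −91 + 1 = −90.

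**Route 2: start day missing, end partial and capped in the same month.** Start and end are both recorded only as August, after the first-dose month. The start becomes 31 August. If death or data extraction is on 10 August, the end becomes 10 August, and the duration is 10 − 31 + 1 = −20. For a cap on day d of a 31-day month the result is d − 30: 0 at d = 30 and −29 at d = 1.

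**Does anything else prevent it?** The re-sorting rule compares end months between records and changes only an imputed start day. Appendix B asks for queries on some missing fields, but Appendix A has no query and no date-order check. A year-only start in the first-dose year, post-dose, goes to the first dose date and cannot invert.

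**What moves downstream.** Route 1 changes only the end date. In route 2 the start stays after first dose. Appendix B therefore classifies the event the same way, and incidence and severity are untouched. Time to resolution runs from the start of the first treatment-emergent episode (SAP 7.6.1.1). A zero or negative time therefore reaches the neuropathy summary only if the event resolved and its first onset, recorded or imputed, is more than 30 days after last dose, or if it falls in route 2.

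**Size in a summary (assumption only; the documents give no frequency).** With onset uniform over days 31 to 100, the mean route 1 duration is 31 − 65.5 = −34.5. Compared with a floor of 1 day, one such event lowers the mean by 35.5/10 = 3.6 days among 10 resolved events, 35.5/20 = 1.8 among 20, and 35.5/50 = 0.7 among 50.

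**The case against.** The best defence is rarity. Route 1 needs a last record, a resolved or fatal outcome, a known start month with an unknown end month, an end year equal to the last-dose year, and onset after day 30. Non-serious AEs are followed only through the reporting period, so a late event would normally resolve within weeks of a recorded onset. Protocol 8.1 and 8.2 also provide CRF review and edit-check queries. SAP 6.1 reports medians as well as means, and one outlier barely moves a median. Finally, a negative duration announces itself, while a floored value of 1 day looks like a genuine next-day recovery.

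Most of this stands as a limit on size. It does not remove the fault: queries reduce partial dates, but the algorithm exists for those that remain, and for these records its answer is impossible. The last argument is a good reason to flag floored records.

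Some stronger readings are tempting but not supported:

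- A reader might infer that negative times spread through the neuropathy summary. They do not. Neuropathy that began on treatment and changed grade late is timed from its first episode, and fatal events do not count as resolved.
- A reader might take 31APR2012 as proof that dates are never validated. The rule says the last day of the month, so the intended date is plain and the misprint is clerical.

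**Conclusion.** The point holds as a specification error of limited reach. Applied as written, Appendix A gives durations of 0 to −69 days for complete onsets on days 31 to 100 after last dose, and lower values when the start day is imputed. It also gives 0 to −29 days by route 2 in a 31-day month. The upper end of the exposure assumes that last dose means the last dose of either drug, that nivolumab was given on that date, and that onset falls in the same calendar year.

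The number of affected records cannot be known from the documents and is probably small. The primary efficacy analysis does not use these dates, and AE incidence, severity and treatment-emergent status do not change.

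A reader might also see the laboratory scope in SAP 7.6.1.2, which mentions results through the EOT visit, as a companion error. That text leaves the window unclear but does not produce an impossible result, and nothing here rests on it.

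**What to change.** Add one sentence to Appendix A: *An imputed AE start date is never later than the date of death or the data extraction date; after that, an imputed AE end date is never earlier than the AE start date.* Apply the start clause after the re-sorting step, because that step can itself move a start day to the month end.

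The order of the two clauses matters. A floor alone would turn the August example into an end of 31 August, after death or extraction. With both clauses, start and end are 10 August and the duration is 1 day. For route 1, every onset on days 31 to 100 gets 1 day. Onsets on days 29, 30, 31 and 32 get 2, 1, 1 and 1, so the floor creates no jump.

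Keep the other imputation rules, including last dose + 30. Moving that cap to last dose + 100 would put route 1 durations at 1 to 70 days for complete starts, but it would also lengthen imputed durations for earlier events that the present rule handles.

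Flag floored records in the dataset and footnote the duration and time-to-resolution tables, because 1 day is a minimum and not an estimate. Correct 31APR2012 to 30APR2012 in Example 2 as a clerical edit.

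The cost is one sentence, one flag variable and a footnote. No new data are needed and site conduct does not change.
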